6.2.2 Prohibited medication

Use of the treatments displayed in the table below are not allowed after the start of the study i.e., Screening. In addition, there are certain washout periods to be respected, as also outlined in the exclusion criteria ([Section 5.2](#)).

Table 6-2 Prohibited medication and procedures

Medication	Prohibition period	Action taken
Study Eye		
Any anti-VEGF drugs or investigational drugs, biologics or devices	Any time	Discontinue study treatment

Medication	Prohibition period	Action taken
Study Eye		
(other than vitamin supplements)		
Any periocular injection or intraocular administration of corticosteroids (except if needed as short term treatment of AE)	Any time	Discontinue study treatment (except if for treatment of AE)
Laser treatment for wAMD (except if needed as short-term treatment of AE)	Any time	Discontinue study treatment
Fellow eye		
Any investigational drug, biologic or device (other than vitamin supplements)	Any time	Discontinue study treatment
Systemic		
Anti-VEGF treatment	Any time	Discontinue study treatment
Any investigational drug, biologic or device (other than vitamin supplements)	Any time	Discontinue study treatment
Medications known to be toxic to the lens, retina or optic nerve, including ethambutol, chloroquine/ hydroxychloroquine, deferoxamine, phenothiazines and tamoxifen (except temporary use for COVID-19 treatment)	Any time	Discontinue study treatment

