6.2.3 Rescue medication

There will be no rescue medication for wAMD in the study eye.

In case of lack of efficacy with investigational drug for wAMD and if the Investigator deems it is in the best interest of the patient to receive prohibited treatment ([Section 6.2.2](#)) in the study eye, the Investigator should follow the instructions for study treatment discontinuation or study discontinuation provided in [Section 9](#).

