9.1 Discontinuation and completion

9.1.1 Study treatment discontinuation and study discontinuation

Discontinuation of study treatment for a participant occurs when study treatment is stopped earlier than the protocol planned duration and can be initiated by either the participant or the Investigator.

The Investigator must discontinue study treatment for a given participant if, he/she believes that continuation would negatively impact the participant's well-being.

Study treatment must be discontinued under the following circumstances:

- Participant decision
- Pregnancy (see [Section 8.4.1](#) and [Section 10.1.4](#))
- Use of prohibited treatment as per recommendations in [Section 6.2.2](#)
- Any situation in which study participation might result in a safety risk to the participant
- Subject develops a retinal vasculitis and/or a retinal vascular occlusion event in the brolucizumab arm
- Unsatisfactory therapeutic effect

If discontinuation of study treatment occurs, the Investigator should make a reasonable effort to understand the primary reason for the participant's premature discontinuation of study treatment and record this information.

Participants who prematurely discontinue study treatment for any reason, except for withdrawal of consent (refer to [Section 9.1.2](#)), should continue in the study with all the scheduled visits and assessments (except disease activity assessment, administration of study treatment, post-injection assessment and adherence to prohibited medication list) until Week 48, at the discretion of the Investigator or the participant. If a participant discontinues study treatment before Week 16 (visit 6), he/she will complete monthly visits until Week 16 (visit 6) and after Week 16 he/she will continue with bimonthly visits until Week 48.

Participants who decide not to participate in the study further should NOT be considered withdrawn from the study UNLESS they withdraw their consent (see [Section 9.1.2](#)). **Where possible, participants should return for the Week 48 (end of study) assessments to be performed as indicated** in the Assessment Schedule ([Table 8-1](#)). If they fail to return for these assessments for unknown reasons, every effort (e.g. telephone, e-mail, letter) should be made to contact the participant/pre-designated contact as specified in the lost to follow-up section.

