| 3. To evaluate the effect of brolucizumab on the evolution of functional parameters of wAMD from Baseline to Week 48 | 3. BCVA ETDRS Score | 3. Change in BCVA from Baseline up to Week 48 |
| 4. To evaluate the effect of brolucizumab on sustained dryness from Baseline to Week 48 | 4. SD-OCT dates, Intraretinal fluid (IRF) and Subretinal fluid (SRF) | 
4. Time to reach sustained dryness of the study eye, as defined by the absence of IRF and SRF for at least 2 consecutive visits and for at least 3 consecutive visits
 
4. Cumulative incidence of sustained dryness of the study eye, i.e. the absence of IRF and SRF for at least 2 consecutive visits and for at least 3 consecutive visits
 |

| | |
|--|---|
| | Statistical Analysis Plan |
| | Sponsor: Novartis Protocol: CRTH258AIT04 |

| OBJECTIVES | VARIABLES | ENDPOINTS |
|--|---|--|
| 5. To evaluate the reasons underlying the Investigators' choice of brolucizumab treatment regimen (q21w or q8w) at Week 16 | 
5. Parameters considered to assess the presence of disease activity:
 
 • BCVA • Leakage at FA/ICGA • Central Subfield Thickness (CST) at SD-OCT • Intraretinal fluid (IRF) at SD-OCT • Subretinal fluid (SRF) at SD-OCT • Subretinal pigment epithelium (sub-RPE) fluid at SD-OCT • Retina Pigment Epithelial Detachment volume at SD-OCT • Central Retinal Thickness (CRT) • Subretinal hyperreflective material (SHRM) at SDOCT • CNV size at OCTA • Vessel density at OCTA • Vessel morphology at OCTA • Hemorrhage at CFP • Other | 5. Determinants in the Investigator's choice of brolucizumab dosing regimen (q12w or q8w) at Week 16 (i.e. BCVA, IRF, SRF, sub-RPE fluid, presence of hemorrhages, CRT, OCTA anatomical parameters and/or 3-field CFP) |
| 6. To evaluate anxiety/depression in patients with wAMD treated with brolucizumab | 6. HADS questionnaire | 6. Change in Hospital Anxiety and Depression Scale (HADS) scores from Baseline to Week 48 |
| 7. To evaluate quality of life in patients with wAMD treated with brolucizumab | 7. EuroQol-5D-5L questionnaire | 7. Change in EuroQol-5D-5L (EQ-5D-5L) scores from Baseline to Week 48 |

| | |
|--|---|
| | Statistical Analysis Plan |
| | Sponsor: Novartis Protocol: CRTH258AIT04 |

| OBJECTIVES | VARIABLES | ENDPOINTS |
|--|-------------------|--|
| 8. To assess the safety and tolerability of brolucizumab | 8. Adverse Events | 8. Incidence of Ocular and Non-ocular AEs throughout the study |

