4.4.3. Handling of Drop-Out Patients

Drop-out patients will be included in the analysis based on available assessments.

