6.3.2. Secondary efficacy analysis

All secondary efficacy analyses will be based on the Safety Set. The analyses performed at eye level will focus on the study eye only.

6.3.2.1. *Optical coherence tomography angiography (OCTA) parameters*

Definition

Optical Coherence Tomography Angiography (OCTA) is a non-invasive imaging modality that provides cross-sectional, three-dimensional and high-resolution imaging of the retinal and choroidal vasculature with micrometer-scale depth resolution. It does not require any dye injection and allows the retinal and choroid vessels to be viewed dynamically.

Optical Coherence Tomography Angiography (OCTA) images will be obtained and assessed in the study eye at every study visit and in the fellow eye at Screening and Week 48. The OCTA images will be evaluated by the CRC considering only images on study eye during the study (except screening visit). The OCTA images on fellow eye and on study eye at screening will be only stored but not grading.

On OCTA images grading by CRC, the following qualitative parameter will be measured:

- Branching vessels: evaluate the width of vessel respect to previous read. The presence of tiny vessels branching from bigger vessels is indicative an active CNV lesion. The possible values will be 'increased from prior' (i.e., possible active CNV lesion), 'decreased from prior', 'stable', 'N/A (baseline)' (of note, this will be expected for baseline since there is not a previous image to be compare), 'UNG/P', 'UNG/Q'.
- Peripheral Anastomotic Arcades: possible values will be 'No', 'Yes', 'UNG/P', 'UNG/Q' and in case of presence (i.e., 'Yes') of peripheral anastomotic arcades at the vessel termini is indicative of an active CNV lesion.
- Vascular Loops: possible values will be 'No', 'Yes', 'UNG/P', 'UNG/Q'. The presence of vascular loop (i.e., anatomical anomalies) is indicative of an active CNV lesion.
- Dark Halo: possible values will be 'No', 'Yes', 'UNG/P', 'UNG/Q'. The presence of dark halo that are hypointense area considered as a region of choriocapillaris alteration, corresponding to local flow impairment and is indicative of an active CNV lesion.

| | |
|--|----------------------------------|
| | Statistical Analysis Plan |
| | Sponsor: Novartis |
| | Protocol: CRTH258AIT04 |

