6.3.2.4. Sustained dryness

Definition

Firstly, the proportion of patients with fluid present at baseline will be identified as patients with IRF or SRF equal to "Yes" at baseline and it will be presented together with the distribution of patients in the following categories: patients with only IRF present at baseline, patients with only SRF present at baseline and patients with both IRF and SRF at baseline.

Among patients with fluid present at baseline, patients with fluid resolution will be identified in case of absence of IRF and SRF and patients without fluid resolution will be also categorized in 'Only IRF present', 'Only SRF present', 'Both IRF and SRF present' at each post-baseline applicable timepoint from Week 8 to Week 48 considering patients who performed SD-OCT at the corresponding timepoint. Then patients who achieved the sustained dryness will be identified considering patients with fluid resolution for at least 2/3 consecutive visits.

| | |
|--|---|
| | Statistical Analysis Plan |
| | Sponsor: Novartis Protocol: CRTH258AIT04 |

For each possible timepoint from Week 8 to Week 48, the sustained dryness will be evaluated considered the SD-OCT assessment as follows:

- If patient perform the visit: the assessment done at the specific timepoint and the previous one performed.
- If patient does not perform the visit: the previous 2 assessments performed will be considered.

The time to achieved sustained dryness is defines as the time, in weeks, from the first injection (i.e., baseline visit) to the earliest post-baseline SD-OCT assessment date on which the first sustained dryness is reached. If a patient does not achieve sustained dryness, the time will be censored at the date of last SD-OCT assessment.

Time to sustained dryness is computed as:

$$(\text{event}/\text{censoring date} - \text{first injection date} + 1)/7$$

where event date is SD-OCT date in which the first sustained dryness is reached while censor date is the last SD-OCT date.

Analysis methodology

Firstly, a description of the proportion of patients with IRF or SRF present at baseline will be provided. On these patients a description of the proportion of patients with fluid resolution, defined as absence of IRF and SRF fluid, will be provided at each timepoint considered the number of patients who perform each visit. A graphical representation (bar graph) will be also provided.

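### Sustained dryness first reached on another anti-VEGF drug, after brolucizumab is stopped, would count as an effect of brolucizumab, because the secondary analyses do not separate post-switch assessments

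*Protocol*

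**What the plan says.** Protocol 9.1.1 asks that participants who stop study treatment, other than by withdrawing consent, "should continue in the study with all the scheduled visits and assessments" up to Week 48, "except disease activity assessment, administration of study treatment, post-injection assessment and adherence to prohibited medication list". This is at the discretion of the investigator or participant. The minimum after stopping is new or concomitant treatments and adverse events, which may be collected by telephone or email. The reasons for stopping include unsatisfactory effect, retinal vasculitis or vascular occlusion, other safety risk, and use of a prohibited treatment.

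For the study eye, the list in Protocol 6.2.2 (Table 6-2) covers "Any anti-VEGF drugs or investigational drugs, biologics or devices". Under Protocol 6.2.3, when the drug lacks efficacy and the investigator judges that a prohibited treatment in the study eye is in the patient's interest, "the Investigator should follow the instructions for study treatment discontinuation or study discontinuation".

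SAP section 2 words the dryness objective as "To evaluate the effect of brolucizumab on sustained dryness from Baseline to Week 48", with parallel wording for the OCTA, SD-OCT and functional parameters. SAP 6.3.2 states: "All secondary efficacy analyses will be based on the Safety Set". Sections 6.3.2.1 to 6.3.2.4 use observed data, with a carried-forward version added for BCVA up to Week 16 only. In SAP 6.3.2.4 the event is the first SD-OCT date on which sustained dryness is reached, and: "If a patient does not achieve sustained dryness, the time will be censored at the date of last SD-OCT assessment". Protocol 2.2 marks secondary estimands as not applicable.

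**The concern.** Read together, these rules create a foreseeable set of study-eye images and BCVA scores taken under another anti-VEGF drug and pass them unmarked into analyses described as the effect of brolucizumab. With one arm, no comparator would reveal the contribution of the second drug.

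Dryness is the most exposed result. A patient who stays wet on brolucizumab, stops, receives another agent and then has two or three consecutive dry visits becomes an event in the Kaplan-Meier curve and a success in the Clopper-Pearson proportion. Post-switch visits also enter the change-from-baseline summaries, paired tests and shift tables for BCVA, CST, SD-OCT and OCTA.

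The SAP recognises the issue elsewhere. It counts treatment discontinuation as failure for the primary outcome (SAP 1.1 and 6.3.1), and it limits the Week 16 regimen-choice analysis to patients still on treatment (SAP 6.3.2.5). The other secondary efficacy endpoints have no rule of either kind.

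**Working it through.** **1. Can the data arise?** Yes, but not for every patient who stops. Protocol 9.1.1 lifts the prohibited list after stopping and continues scheduled imaging, Protocol 6.2.2 shows that the list is what bars other anti-VEGF drugs, and Protocol 6.2.3 describes the route for lack of efficacy. Follow-up is discretionary, may shrink to remote contact, and does not exist for those who leave the study.

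**2. Does any rule remove them?** None was found. The analysis set is not limited to patients on treatment, the data rule is as observed, the dryness censoring date is the last SD-OCT, and sensitivity analyses for these endpoints are marked not applicable (SAP 6.3.2.1 to 6.3.2.4).

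**3. Who can change cumulative dryness?** The event is the first sustained dryness, so a patient already dry for the required visits on brolucizumab adds nothing after switching. Only switchers not yet dry, who still have SD-OCT and then reach two or three consecutive dry visits, matter.

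**4. The plan's own precision, as a yardstick.** The Wald sample size is n = 1.96² × 0.56 × 0.44 / 0.06² = 262.93, which gives the stated 263. At N = 122 and p = 0.50 the full width is 2 × 1.96 × √(0.25/122) = 17.74%, as SAP 3.5 states, so the half-width is about 8.9 points. Both figures concern the primary proportion and serve here only for scale.

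**5. Illustrative size.** Let d be the share of patients who stop, s the share of those who switch and still have images, u the share of those not already dry, and q the share of these who first become dry after the switch. Then the excess in points is 100 × d × s × u × q. The documents give none of these. Setting s = u = 1 (every stopper switches, none was dry) gives a ceiling for each d and q:

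| d (of 122) | q = 25% | q = 50% | q = 75% |
|---|---|---|---|
| 5% (about 6) | 1.25 | 2.5 | 3.75 |
| 10% (about 12) | 2.5 | 5.0 | 7.5 |
| 20% (about 24) | 5.0 | 10.0 | 15.0 |

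Halving both s and u divides every entry by four; the middle entry falls from 5.0 to 1.25. The denominator is also approximate, because SAP 6.3.2.4 assesses fluid resolution among patients with fluid at baseline, who may number fewer than 122.

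**6. How the handling of switchers changes the answer (assumed counts).** Take 122 patients: 88 become dry on brolucizumab, and 12 who are not dry switch, of whom 6 then dry.

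- Switchers counted as not dry: 88/122 = 72.1%.
- All data, as the SAP stands: (88 + 6)/122 = 94/122 = 77.0%.
- Switchers removed: 88/(122 − 12) = 88/110 = 80.0%.

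Removing switchers lies further from the first figure than the current rule does, because it drops the poor responders.

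**7. Direction for BCVA and CST.** A switch made for lack of effect could improve later values. Patients must also stop for retinal vasculitis or vascular occlusion, which Protocol 1.1 says may cause severe vision loss, and others may stop and receive nothing. The net sign cannot be derived.

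**The case against.** The strongest reply is that this is a choice of strategy. Following patients after they stop and using all data is in effect a treatment-policy approach, and with no secondary estimand defined, no declared rule is broken. That stands in part: such an approach would be legitimate if stated. It is not stated, and it fits poorly with objectives worded as the effect of the drug.

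A reader might go further than the documents allow in four ways.

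- **That the secondary results are biased in brolucizumab's favour throughout.** Only the dryness event has a clear direction, since a post-switch event can only add to the count.
- **That dryness is overstated by a definite amount.** Any such figure rests on assumed rates, and the simplest version also supposes that everyone who stops then switches and that none was dry beforehand.
- **That counting one patient as a primary failure and a secondary success is a contradiction.** A patient dry on the q8w regimen is classified that way by design, because the endpoints ask different questions.
- **That SAP 4.4.3 settles the matter.** It says "Drop-out patients will be included in the analysis based on available assessments", but the SAP separates leaving the study from stopping treatment, so the sentence need not cover patients who stop and stay. The point rests on the as-observed rules.

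It is also fair to say that the SAP tabulates treatment discontinuation with reasons (6.1) and ocular concomitant medication by eye (6.4.2). A reader could see how much switching occurred, but not what it did to the efficacy results.

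**Conclusion.** The point holds for attribution: nothing in the plan stops dryness first reached after a switch from being credited to brolucizumab. It is a minor point, because the primary outcome counts treatment discontinuation as failure and so is not exposed. The size is unknown. The tabulated values of 1.25 to 15 points are ceilings under assumed stopping and drying rates; the larger ones match or exceed the 8.9-point half-width, and the true excess is zero if nobody switches before becoming dry. For BCVA, CST and the other imaging parameters, the conclusion is only that post-switch values are mixed in, with no direction established.

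**What to change.** In SAP 6.3.2.4, do not count sustained dryness first reached after a non-study anti-VEGF injection in the study eye. The event date is the visit that completes the dry run, so a run that starts before the switch and is completed after it is also not counted; say so.

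- **Cumulative incidence (Clopper-Pearson):** keep these patients in the denominator as not dry.
- **Kaplan-Meier:** carry them as event-free to Week 48. Give censoring at the switch as a sensitivity analysis, because that censoring may be informative.
- **BCVA, CST, SD-OCT and OCTA changes and shift tables:** report the all-data result beside a version that leaves out post-switch visits. Neither should stand alone, since leaving visits out removes likely poor responders.
- **Reporting:** state the number of switchers and how many were already dry when they switched.

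No new data are needed. Protocol 9.1.1 still collects new treatments after stopping, and SAP 6.4.2 already classifies ocular medications and procedures by eye. The cost is one derived flag, some extra tables, and slightly fewer Week 48 observations in the second version. If the analysis has already been run, label the additions post hoc. The change concerns analysis only and leaves patient management as it is.

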9.1.1.1 Replacement policy

Participants who started treatment, but prematurely discontinued treatment and/or study will not be replaced.

9.1.2 Withdrawal of informed consent

Participants may voluntarily withdraw consent to participate in the study for any reason at any time. Withdrawal of consent occurs only when a participant:

- Explicitly requests to stop use of their biological samples and/or data (opposition to use participant's data and biological samples)

and

- No longer wishes to receive study treatment

and

- Does not want any further visits or assessments (including further study-related contacts)

This request should be in writing (depending on local regulations) and recorded in the source documentation.

In this situation, the Investigator should make a reasonable effort (e.g. telephone, e-mail, letter) to understand the primary reason for the participant's decision to withdraw his/her consent /opposition to use data and record this information.

Where consent to the use of personal and coded data is not required in a certain country's legal framework, participant therefore cannot withdraw consent. They still retain the right to object to the further use of personal data.

Study treatment must be discontinued and no further assessments conducted, and the data that would have been collected at subsequent visits will be considered missing.

Further attempts to contact the participant are not allowed unless safety findings require communicating or follow-up.

If the participant agrees, a final evaluation at the time of the participant's withdrawal of consent/opposition to use data/biological samples should be made as detailed in the assessment table (refer to Section 8).

All efforts should be made to complete the assessments prior to study discontinuation. A final evaluation at the time of the participant's study discontinuation should be made as detailed in the assessment table.

Novartis will continue to retain and use all research results (data) that have already been collected for the study evaluation. No new Personal Data (including biological samples) will be collected following withdrawal of consent/opposition.

9.1.3 Lost to follow-up

For participants whose status is unclear because they fail to appear for study visits without stating an intention to discontinue or withdraw, the Investigator must show "due diligence" by documenting in the source documents steps taken to contact the participant, e.g. dates of telephone calls, registered letters, etc. A participant should not be considered as lost to follow-up until due diligence has been completed or until the end of the study.

9.1.4 Early study termination by the sponsor

The study can be terminated by Novartis at any time.

Reasons for early termination may include, but are not limited to:

- Unexpected, significant, or unacceptable safety risk to participants enrolled in the study
- Decision based on recommendations from applicable board(s) after review of safety and efficacy data
- Discontinuation of study drug development
- Practical reasons, including slow enrollment
- Regulatory or medical reasons

In taking the decision to terminate, Novartis will always consider participant welfare and safety. Should early termination be necessary, participants must be seen as soon as possible and treated as a prematurely withdrawn participant. The Investigator may be informed of additional procedures to be followed in order to ensure that adequate consideration is given to the protection of the participant's interests. The Investigator or sponsor depending on local regulation will be responsible for informing IRBs/IECs of the early termination of the trial.

